The OT will receive 15 hours of core didactic training on the pathophysiology and treatment of DM (Drs. [name] and [name]). The OTs will be trained to deliver occupational therapy in accord with the study protocol and to provide DSM education using the BA treatment paradigm. To accomplish this, Drs. [name], [name], and [name] will jointly train the OTs, emphasizing skill development and providing supervised training with the goal of integrating DSM and occupational therapy within the BA treatment paradigm. This aspect of the training will consist of a day long workshop, which will include readings, didactic and experiential sessions, and conducting supervised role-play treatment sessions. [name] will provide didactic instruction in BA theory, review the PC-OT treatment manual, and session procedures. [name] will continue DSM education and skills training, including review of core DM knowledge/skills training (i.e., monitoring of blood glucose and implementing intervention protocols) and community resources to assist the PC-OT interventionists in developing Action Plans to enable participants to achieve DSM goals. [name] will review the major strategies/skills employed by OTs for improving medication management. She will also provide education on MCI and will review techniques for overcoming barriers related to impaired memory. [name] will also train the OTs to conduct the OT assessments to be administered to determine current ability to manage medication [Allen Cognitive Level Screen, Allen Diagnostic Module, Performance Assessment of Self-care Skills (PASS)-Medication Management Task, Safety Assessment of Function & the Environment for Rehabilitation Tool (SAFER)].

[name] will also review procedures to maintain treatment fidelity, treatment documentation (e.g., specifics of Action Plans, strategies imparted to participants, devices/aids dispensed), and maintenance of treatment records and adherence to protocols. [name] will discuss the realities of delivering DSM education and training in the community (i.e., logistical and social barriers encountered in conducting home visits).

Following these formal training experiences, we will assign each OT 5 training cases to be treated consecutively for 5 sessions. Drs. [name], [name], and [name] will supervise the training cases by reviewing and rating recordings of the first, third and sixth sessions and use standardized monitoring checklists developed for this study (see Appendix). Then each supervisor will provide feedback following each of these rated sessions. The OT interventionist must meet satisfactory levels of competence on his/her training cases before starting the clinical trial. The OTs (along with the outcome assessor and the research assistant) will also receive training on Jefferson's Electronic Medical Records (EMR) system (to be conducted by [name]).

3. Community Health Worker (CHW) training

The CHW will deliver all EUC sessions to participants randomized to the control group. To develop the CHW's knowledge-based and skills-based competencies, we will provide core

Version 4 (Jan 2015)

didactic and experiential training, including reviewing the pathophysiology and treatment of DM (Drs. [name] and [name]), management of DM in the community (Drs. [name] and [name]), and the treatment protocol (Drs. [name] and [name]). [name] will also train the CHW in the principles and delivery of supportive therapy to control for the effects of attention.. The CHW will be required to deliver EUC to 3 training cases, which will be reviewed by Drs. [name] and [name].

4. Outcome Assessor training

Drs. [name] and [name] will review general interviewing techniques (e.g., establishing rapport, maintaining structure, completing paperwork, and managing time), and procedures for obtaining informed consent. [name] will review each study instrument to ensure that the assessor understands all items and measurement intent. The assessor will administer assessments in-person (i.e., with the participant) and will enter all data directly onto a laptop. Prior to entering the field, the Assessor will conduct 5 practice baseline assessments that will be audio recorded. [name] will review the recordings and provide feedback to the assessor on her performance and protocol adherence. Thereafter, we will hold 2 meetings per month to review recent cases, test administration procedures, and coding decisions to ensure accuracy and minimize assessor drift. [name] will review procedures for collecting blood samples, including safety issues, proper storage, labeling samples, and transporting samples to the lab.

5. Research assistant (RA) training

The RA will be responsible for conducting the run-in visits and monthly MEMS data collection. [name] will provide training on conducting these visits and using the MEMS bottles/caps and electronic reader. The RA will be trained on how to calculate the run-in adherence rate.

CHAPTER 8. DESCRIPTION OF INTERVENTIONS

PC-OT:

PC-OT aims to improve glycemic control by increasing medication adherence and improving other DSM practices. Treatment addresses medication adherence first, and then moves onto other aspects of DSM. PC-OT consists of 4 major elements: 1) PCP-OT collaboration; 2) DSM education tailored to cognitive impairment; 3) standard OT cognitive-functional assessment; and 4) OT-delivered Behavior Activation (BA) to develop and reinforce treatment plans. Treatment plans are designed to compensate for cognitive and physical deficits, anchor drug administration to daily routines (e.g., mealtimes, personal hygiene), incorporate personal values and beliefs, recognize social realities (e.g., competing caregiving responsibilities), and capitalize on procedural memory, which refers to learning behaviors that are enacted automatically. Procedural memory remains intact relative to episodic memory (i.e., delayed recall) in MCI, as the 2 memory systems have different neural substrates. The OT builds on this retained capacity when developing medication adherence (e.g., linking medication-taking to daily routines) and other DSM adherence plans.

1. PC-OT Collaboration: The OT and the PCP will have a minimum of 4 EMR communications. They begin by reviewing a participant's medications and when they should be taken, identify evidence of polypharmacy, and discuss a participant's target HbA1c, given his/her current HbA1c ≥ 7.5 and $\leq 80\%$ adherence. The PCP will decide if: 1) the OT will increase adherence to the current regimen (likely if the participant takes metformin); or 2) the PCP will change the regimen (e.g., reduce sulfonylurea dose) to avoid hypoglycemia, anticipating that better adherence will lower blood glucose. The PCP will also inform the OT of relevant medical factors (e.g., comorbidities, exercise limitations) that may influence DSM. The OT will then begin in-home evaluation and treatment. After the 3rd session, the OT will inform the PCP via the EMR of the medication adherence Action Plans (e.g., linking medication-taking to morning routines, organizing medications), and convey any question a participant has about their medications (e.g., possible side effects). The PCP will respond, approve, or modify the plan via the EMR. In subsequent contacts, the OT and PCP will discuss treatment progress and Action Plans to improve diet and exercise. The PCP will reinforce Action Plans with participants during office visits (about every 3 months). The OT will update the PCP after the 5th session, and after each of the 3 booster sessions. The OT will inform the PCP of clinical (e.g., persistent depression) or treatment information (needs prescription refill). The PCP will respond and post incident health events and needed health screens for the OT to include in future Action Plans

2. DM Education: The OT will provide DM education throughout the intervention to build knowledge and skills (e.g., blood sugar monitoring) according to national standards. The OT will review the NIH publication, *"4 Steps to Control your Diabetes for Life"* and *"Project DECIDE"* (Decision-making Education for Choices In Diabetes Everyday) educational materials. Previous studies have demonstrated the value of the latter materials in older AAs with DM and cognitive impairment. The OTs will tailor the education to participants' cognitive strengths and deficits. They will respect participants' learning pace as they introduce new information and use repetition and "reflecting back" (i.e., asking participants to state what they understand in their own words) to ensure adequate understanding.

3. Cognitive-Functional Assessment: Medication adherence involves participant (e.g., cognition, beliefs), environmental (e.g., disorganization), and contextual (e.g., competing social demands)

factors. The OTs will assess these factors, drawing from baseline data (i.e., health beliefs, cognitive tests, current DSM practices) and their formal evaluations, to tailor the treatment plan. For example, the OT may identify environmental barriers (e.g., medications stored in different rooms) that inhibit medication adherence, and then suggest strategies to mitigate their impact. Or the OT might identify health perceptions that compromise adherence. For example, the OT might say, “At the baseline interview, you said you take metformin only when you feel woozy. You might feel less woozy if you take it every day. Are there reasons you prefer not to? Let’s talk about them and see if we can help you take your medications the way your doctor thinks is best for you.” In this way the OT identifies perceived obstacles [e.g., costs, side effects, beliefs, depression, transportation, and distractions (e.g., visiting family) that can be addressed in the treatment plan.

The OT then administers the Allen Cognitive Assessment battery, which is a standardized performance-based assessment that grades information processing and visuo-motor abilities (e.g., following directions, problem-solving, learning potential, cueing needs) and links activity demands to performance skills. The OT uses the Allen to identify participants’ cognitive-functional capacities in order to select strategies that build on the participant’s best abilities. The OT also administers the Performance Assessment of Self-care Skills-Medication Management Task to evaluate specific physical (e.g., upper extremity motor/sensory function, dexterity) and cognitive aspects of medication-taking (e.g., efficiency, safety awareness, and performance quality). Based on these assessments, the OT will determine if participants are intentionally nonadherent (due to side effects, costs, or misperceptions about their medications), occasionally but not intentionally miss doses, or lack cognitive or motor capacity to adhere adequately. This determination will guide the selection and tailoring of intervention strategies (e.g., environmental cues to help sequence a task). As needed, the OT will suggest referral to the Area Agency on Aging to ensure that basic needs are met to support effective DSM.

4. OT-delivered Behavior Activation (BA):

a) Medication Adherence: The OT and participant begin by reviewing all medications, their purpose, and dosing instructions. They devise a plan to integrate medication-taking into daily routines (e.g., take metformin after making coffee), involve caregivers if available, and use environment adaptations and memory aids to increase adherence. The OT draws from 3 broad rehabilitative strategies: 1) activity simplification (e.g., break down complex activities into component tasks; 2) environmental modification (e.g., visual cues like reminder cards, strategic placement of medications, reduce clutter, improve lighting); and 3) device use (e.g., pill organizers, magnifiers, talking watch with reminders). For example, visual cues (e.g., placing morning medications by coffee maker) might be linked to the verbal messages (e.g., “I turn on the coffee maker, take my pills, and mark the check sheet on the refrigerator.”). Once the OT is sure the plan is feasible, the OT uses BA to reinforce and routinize the plan. BA involves: 1) developing Action Plans that define the plan goal and the steps to achieve it; and 2) recording completion of the steps on a checklist. The steps need to be observable, quantifiable, and easy enough to succeed to provide positive reinforcement. In subsequent sessions, the OT evaluates the success of the Action Plan and modifies it if necessary.

The OT does not manage medication dosing or put medications in pill organizers. Instead, they help the participant establish a routine for medication management that is supported by the home environment and accounts for personal, cultural, and social influences. If there are problems with medications (e.g., confusion about dosing schedule), the OT works with the PCP to resolve them, and then works with the participant to determine the best adherence strategy. If pills need to be

Version 4 (Jan 2015)

transferred from one container to another, the OT provides the needed structure and supervision based on the prescription and communication with the PCP, which reinforces the skills necessary to adhere to medication regimen. To prevent the intervention from confounding MEMS measurement, the OT strictly avoids any instruction on or assistance with MEMS. Although OTs may incorporate the MEMS medication into a general adherence plan (e.g., place all medications in the kitchen), they provide no specific instruction/assistance with MEMS beyond that.

b) Other DSM Practices: In subsequent sessions the OT develops BA Action Plans to improve other DSM practices. Action Plans for diet might include reducing soft drink consumption, eating 3 vegetables/day, eliminating table salt, reading food labels, and using the plate method to balance food portion by food group. For exercise, Action Plans might include using a pedometer to monitor/increase physical activity, doing chair exercises 3 times/day, walking to church). Glucose monitoring plans might include finger sticks linked to meals, or keeping glucose tablets in purse to treat hypoglycemia. The OT will provide skills training as needed (e.g., using a glucometer, plate method to organize meals).

5. Booster Sessions (Months 6, 8, and 10): Scheduling booster sessions will sustain the therapeutic relationship and treatment gains and reduce attrition. The OT will administer 3 in-home booster sessions to reinforce medication adherence and other DSM activities. Prior to each session, the OT will review the EMR to identify changes in a participant's health or medications. If a participant starts insulin, the OT will address that in the treatment plan. The OT and participant will review Action Plans from previous sessions, identify obstacles, and modify Action Plans to accommodate changes in cognition, health, medications, or social circumstances. The OT also provides information on resources to address future needs.

Enhanced Usual Care (EUC):

The control treatment is EUC, which is comprised of "Usual Care" (i.e., routine PCP-delivered medical care) that is "Enhanced" with in-home, low-intensity education and support delivered by a bachelor's level Community Health Worker (CHW). The education component aims to increase DM knowledge and controls for the nonspecific effects of the in-home OT visits. Similar interventions, delivered by lay educators, lead to modest increases in glycemic control in ethnic minorities and are congruent with the American Association of Diabetes Educators' position statement on the role of CHWs in community care of persons with DM. In this RCT, EUC exceeds usual care in its individual attention to participants and use of DM educational materials specifically designed for older AAs with cognitive impairment. The CHWs will meet with participants in their homes at the same frequency and intensity (including booster sessions) and use the same educational materials as the OTs but the CHWs will not interact with PCPs, access the EMR, or develop Action Plans to increase medication adherence or other DSM practices. During each treatment session, the CHW will review core aspects of DM using the written materials to structure the sessions. The CHWs will also facilitate participants' personal expression about the impact of memory loss, DM, and aging on their lives.

CHAPTER 9. ADVERSE EVENTS AND ALERTS

1. Serious adverse events

In providing oversight to human subject safety we distinguish between an Alert and a Serious Adverse Event. We consider an Alert to be a dangerous situation discovered to exist by a member of the research team that is not related to the conduct of the research study. Alerts are not specific to or consequences of the study but represent situations that may be encountered in any interaction with a participant in a home. An example of an Alert may be a hazardous home condition (e.g., no fan or air conditioning and windows unable to open in summer where the home reaches temperatures over 100 degrees).

As per the IRB at TJU, we will report Serious Adverse Events (SAE) (study related or otherwise) to the IRB within 48 hours of learning of an event. Examples of SAEs include in-patient hospitalization, emergency room visits, or any other event that significantly impacts a patient's health status.

2. Documentation

For an alert, documentation involves notifying designated members of the research team (PI and project director) and completing an Alert Event Reporting Form within 24 hours of occurrence of the event. The reporting of alerts to the IRB of TJU is not required.

For a serious adverse event, documentation involves notifying the PI and project director immediately, completing the TJU IRB Serious Adverse Event form, and notifying the TJU IRB within 48 hours of occurrence. Although this is a minimal risk study, all study personal will be trained in these alert and serious adverse event procedures.

The PI will be informed of alerts, actions taken, and resolution. For a serious adverse event, the PI will be notified as soon as the event occurs, either by telephone from the participant's home or immediately there after.

CHAPTER 10: DATA MANAGEMENT

1. General issues

All assessment forms will be created in Teleform, which is a tool whereby data collected in the field are entered directly into a computer. This will be accomplished as follows. The OA will take a laptop computer to all in-home assessments. The computer will prompt the OA to ask each question and enter the participant's response directly into the computer. Immediately after the assessment, the OA will back up the completed assessment on a memory stick. Weekly, the OA will meet with the project director to turn over electronic copies of assessments that were completed the previous week. The electronic copy will be stored on the project director's hard drive, and added to the ongoing database of all participants' completed assessments. The advantages of this method are: (1) it eliminates the need for a data entry person; (2) that skip patterns are built into the program, minimizing this type of data entry error; and (3) the computer signals the OA when questions are skipped or out-of-range values are entered. The OA will bring a back-up computer battery to all assessments. Further, the OA will also bring a blank hard copy of the assessment should the computer malfunction. All computers used for data collection and storage will be encrypted and password protected. The following data will be collected with written forms which will be entered by hand: (1) intervention notes; (2) intervention forms; and (3) data collected from the EMR.

Data management and cleaning will be ongoing throughout the study. Inconsistencies and missing data will be reconciled (e.g. call participant or check EMR for missing data). We will create a separate database for each time wave. Participant identification numbers will be used to link data from multiple time points for longitudinal analyses. On a monthly basis, the project director will run frequency distributions for all variables to check for accuracy. We will perform weekly back-ups of all databases in triplicate.

Although we will take careful efforts to minimize missing data, we will handle missing data in the following way: at each time point, participants who complete that assessment will be compared to those lost to attrition on all baseline variables as well as those from previous time points if appropriate. Any variable(s) that emerge as significantly different will be controlled statistically.

2. Description of computing environment

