The adherence rate will be determined by the percent of pills that were taken on time. The instructions on the pharmacy label will be used to determine the number and timing of pills to be taken each day. If a participant only takes 1 dose daily, and no time is specified on the label, the RA will ask the participant what time they typically take the pill. This time will be designated as the Target Time. If the label indicates that multiple daily doses should be taken (and no time is listed), the participant will be asked for the times that they usually take each dose to determine the Target Time of each dose. If the label specifies specific times, these times will be the Target Times. To be considered as "on time", a pill must be taken within 4 hours of the Target Time. Days in which the participant did not open the MEMS bottle due to out of the ordinary circumstances (e.g., hospitalization) will not be counted when computing the adherence rate. All participants will be given a MEMS log to write down such situations. In addition, at the second run-in visit, the RA will ask participants if there were any unusual circumstances that interfered with medication taking. At each MEMS reading visit, participants will be asked if the time(s) that they take their Target Medication have changed, and if so, the adherence rate for that particular reading will be adjusted accordingly.

Once it is established that the run-in adherence rate is <80% and the participant agrees, the RA will inform [name] that the participant should be randomized. Randomized participants will be instructed to put any refills for the Target Medication in the MEMS bottle.

2. Assignment of study identification numbers

Study identification numbers will be assigned immediately after enrollment. The identification number will consist of a 3 digit number chosen from a consecutive list. All data forms will also contain the participant's 3 initials (the first letter of the first, middle, and last names). If the participant has no middle name, an X will be used. Identification numbers and initials will be used to cross reference

CHAPTER 5: SCHEDULE AND OVERVIEW OF DATA COLLECTION

1. Overview

The Outcome Assessor will conduct assessments at baseline, and 6 and 12 months post-baseline masked to treatment assignment in participants' homes. Below we describe all of the study instruments. Table 2 describes how each measure will be used to assess the study aims.

2. Description of Study Measures

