Medication Adherence: We will assess adherence to the Target Medication with Medication Event Monitoring System (MEMS). MEMS are electronic monitoring caps that electronically record the date and time of medication bottle openings. Research studies indicate that MEMS use does not influence adherence. Because MEMS caps are costly, we will measure adherence to one oral hypoglycemic medication, which participants will identify as the one they are prescribed at the highest dosing frequency. We will also ask participants to keep a MEMS log to report unintended or missed openings (e.g. early pill removal to be taken later in the day) or prolonged non-usage (e.g., if hospitalized). MEMS adherence to a single medication correlates highly with adherence to other medications. For randomized participants, we will download MEMS data every month for 12 months. Prior to each monthly MEMS data download visit, the study coordinator will logon to EMR to see if the participant’s Target Medication dose was changed. If she detects a medication change, she will ask the RA to visit the participant at home to ensure that he/she makes the appropriate adjustment. For example, if the MEMS-monitored drug is discontinued, the RA will ensure that the newly prescribed drug is placed in the MEMS bottle. We will also ask participants to call the study coordinator if the PCP makes any medication changes.

We will assess self-reported adherence with the Morisky Medication Adherence Scale (MMAS). The MMAS is a widely used, validated self-report medication adherence instrument. Scores range from 0 to 4, with higher scores indicating better adherence. In adults with DM (37% AA), Morisky scores ≥ 3 were associated with a 10% lower HbA1c level. Although self-reports often overestimate actual adherence and are biased by memory problems, self-reports are commonly used in clinical practice and will provide a useful comparison to MEMS data.

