5. Malfunctioning MEMS caps

We will run a test on all MEMS caps before distributing them to participants to insure that they are functioning correctly. Participants will be instructed to be sure that the MEMS bottle/cap does not get wet, and to be sure that the cap is tightly closed after each opening. Participants will also be given a log to record "curiosity openings", episodes of "pill pocketing", episodes of not being in control of medication management (e.g., hospitalization), and any other event that may bias adherence rates. All adherence rates will be adjusted for such circumstances.

CHAPTER 7: CERTIFICATION PROCEDURES

1. Certification in the Protection of Human Subjects

As per the regulations of the Institutional Review Board (IRB) at Jefferson, all study staff are required to be trained and certified in the practices of human subjects research. The training is done through the Collaborative Institutional Training Initiative (CITI).

2. PC-OT interventionist training

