Analyses: MEMS adherence data will be summarized as “percentage adherence” during each month. We will model the longitudinal trajectory of post-randomization adherence data using mixed effects linear regression. Fixed effects will be time, randomization assignment, time by randomization interaction, run-in phase adherence, age at randomization, and baseline HbA1c. Random intercept and time effects and an appropriate residual error covariance structure will be assumed to account for within-subject correlation. For purposes of this analysis, we will treat time categorically as a 4 level variable (months 1-3, months 4-6, months 7-9, and months 10-12). Thus, we will have 3 repeated measurements of adherence for each time period. Within this model, we will estimate the average adherence by randomization group during months 4-6 and months 10-12 and test for differences between groups. Supplemental adherence measures (i.e., Morisky Self-Report, Proportion of Days Covered) will be analyzed using a mixed effects model similar to that used for the continuous HbA1c analysis above.

Aim 4: Determine if increasing MEMS-adherence to an oral DM medication mediates PC-OT’s impact on HbA1c levels at 6 and 12 months.

Hypothesis: PC-OT will reduce HbA1c level to the extent that it increases MEMS-adherence to an oral DM medication at 6 and 12 months.

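### The MEMS exclusion rule drops unopened days but keeps on-time openings from the same unusual episode, so measured adherence is overstated whenever an episode contains both

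*Combined protocol and SAP*

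**What the plan says.** Chapter 4, section 1 (Participant recruitment) defines the measure: "The adherence rate will be determined by the percent of pills that were taken on time", where to be on time "a pill must be taken within 4 hours of the Target Time". It then gives the exclusion: "Days in which the participant did not open the MEMS bottle due to out of the ordinary circumstances (e.g., hospitalization) will not be counted". The circumstances come from the participant: "All participants will be given a MEMS log to write down such situations", and at the second run-in visit "the RA will ask participants if there were any unusual circumstances that interfered with medication taking".

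Two other places bear on the same scoring. Chapter 5, section 2 (Medication Adherence) asks participants to "keep a MEMS log to report unintended or missed openings", for example a pill removed early to be taken later, and prolonged non-use. Chapter 6, section 5 (Malfunctioning MEMS caps) has the log cover curiosity openings, pill pocketing, times when the participant did not control the medicines, and "any other event that may bias adherence rates. All adherence rates will be adjusted for such circumstances".

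The resulting rate decides run-in eligibility. It is also a covariate in the HbA1c models (Chapter 11, Aims 1 and 2) and the Aim 3 outcome ("MEMS adherence data will be summarized as “percentage adherence” during each month"), and it is the Aim 4 mediator.

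**The concern.** Whether a day counts should be settled without looking at what happened on that day. Here it is not. Within one unusual episode, a day with no opening is removed, while a day with an on-time opening meets no exclusion condition and stays in both numerator and denominator.

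Hospitalization is given only as an example. No list of qualifying circumstances is provided, no check of the reported reason is required, and the information comes from the log or recall of people with mild cognitive impairment. A miss that is really non-adherence can therefore be attributed to an unusual event and leave the denominator.

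At stake are who is randomized (an inflated run-in rate screens out people who should qualify), the accuracy of the run-in covariate, the Aim 3 adherence estimates and the Aim 4 mediator.

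**Working it through.** **Plan figures.** The documents give no expected MEMS adherence, no frequency of unusual days and no share of misses excused. There is no stated figure to reproduce, and every input below is an assumption unless marked otherwise.

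**Setup (one dose a day).** Let p be the on-time rate on ordinary days, q the share of days in unusual episodes, and a the on-time rate on those days. Days in the episode without an on-time opening are taken as unopened.

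- All days count: A = (1−q)p + qa
- Whole episode excluded: B = p
- Literal Chapter 4 rule: C = [(1−q)p + qa] / [(1−q) + qa]
- Overstatement against whole-episode exclusion: C − B = qa(1−p) / [(1−q) + qa]

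The last expression is never negative, and it is zero when a = 0.

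**A small record.** In a 14-day run-in, 8 of 11 ordinary days are taken and 1 of 3 unusual days is opened on time. All days: 9/14 = 64.3%. Whole episode excluded: 8/11 = 72.7%. Literal rule: 9/12 = 75.0%. Most of the rise comes from excusing the episode at all; the one-sidedness adds 75.0 − 72.7 = 2.3 points.

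**Size of the one-sidedness, C − B in points.**

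| q | p | a = 0 | a = 30% | a = p |
|---|---|---|---|---|
| 5% | 75% | 0 | 0.4 | 1.0 |
| 5% | 60% | 0 | 0.6 | 1.2 |
| 10% | 75% | 0 | 0.8 | 1.9 |
| 10% | 60% | 0 | 1.3 | 2.5 |

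Lowest non-zero cell: 0.05 × 0.30 × 0.25 / 0.965 = 0.0039. Highest: 0.10 × 0.60 × 0.40 / 0.96 = 0.025.

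**Run-in eligibility when misses are excused.** This is the second route: behavioural misses attributed to unusual events. With 14 once-daily doses, K ~ Binomial(14, p) are on time. Each miss is excused with probability u, so E ~ Binomial(14−K, u), and the measured rate is K/(14−E). Exact P(rate ≤ 80%):

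| True adherence | u = 0 | 10% | 20% | 30% |
|---|---|---|---|---|
| 75% | 72% | 64% | 55% | 46% |
| 60% | 96% | 93% | 88% | 81% |

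The plan states the criterion both as ≤80% and as <80%; the strict form changes these figures by little more than 1 point at most. One excused miss can be decisive: 11/14 = 78.6% qualifies, 11/13 = 84.6% does not.

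**Difference between arms.** All figures are in points, PC-OT minus EUC.

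- Same q and same a in both arms: the difference is multiplied by (1−q)/[(1−q)+qa]. At q = 10% and a = 30%, 0.90/0.93 turns 15.0 into 14.5.
- a = p, q = 10% in both arms: 75% v 60% gives 76.9 − 62.5 = 14.4, but 50% v 35% gives 52.6 − 37.4 = 15.2.
- a = p with q differing by arm (75% v 60%, true 15.0): 10% in PC-OT and none in EUC gives 16.9; the reverse gives 12.5.
- Excused-miss form, p/[1−(1−p)u], at u = 10%, 20% and 30%: 75% v 55% (true 20) gives 19.3, 18.5 and 17.5, but 45% v 25% (true 20) gives 20.6, 21.2 and 21.6.

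**The case against.** The strongest reply has four parts.

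1. In the plan's own example there is no bias: a hospitalized participant's home bottle is normally not opened, so the literal rule equals whole-episode exclusion. This stands.
2. The rule requires an unusual circumstance, and the plan does not say that every answer to the research assistant's question excuses a miss. The catch-all in Chapter 6 is tied to events that may bias the rate and sits among measurement artefacts. A reader might infer that any missed dose with a reason is deleted; the text does not go that far. It does leave the boundary undefined.
3. Chapter 6 speaks of episodes and promises that all rates will be adjusted, including for curiosity openings, so adjustment is not only upward and might cover the opened days. It might, but no method is given. Chapter 4 has the only operative exclusion rule, and that rule is one-sided.
4. The metric is on-time doses, so late openings, and missed doses on partly opened days, remain as misses. Not everything that stays is a success. This also stands, and it limits the bias.

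The run-in figures are largest near the cut-off. At true 60% adherence the loss is much smaller, which is why both rows are shown.

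**Conclusion.** The literal Chapter 4 rule makes exclusion depend on the day's outcome, and nothing in Chapters 5 or 6 removes the opened days. The bias in the MEMS rate is upward or nil, and nil where the bottle is never opened in the episode. Its size rests on assumed inputs: about 0.4–2.5 points from the one-sidedness if 5–10% of days are unusual, adherence is 60–75% and a runs from 30% to p. The run-in consequence is larger if 10–30% of misses are excused: a pass probability of 64% down to 46% instead of 72% at true 75%, and 93% down to 81% instead of 96% at true 60%.

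A reader might infer that the rule shrinks the PC-OT versus EUC difference. The documents do not support that. The direction depends on the adherence level, which the plan does not give, and on whether participants, who know their arm, report circumstances differently by arm. Nor does the point reach the HbA1c outcome itself, which does not use MEMS; the run-in rate enters those models only as a pre-randomization covariate. What is affected is run-in eligibility, that covariate, the Aim 3 outcome and the Aim 4 mediator. The matter is worth correcting because the change is cheap, not because the expected bias is large.

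**What to change.** Reconcile the statements in Chapter 4 section 1, Chapter 5 section 2 and Chapter 6 section 5 into one scoring rule:

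- Define a qualifying episode in advance as a dated interval when the participant did not control the medicines, with dates from the log, checked against the EMR where possible.
- Remove every scheduled dose in that interval from both numerator and denominator, whether or not the bottle was opened.
- Keep the logged corrections for early removal, pill pocketing and curiosity openings.
- Count all other unopened scheduled doses as missed.

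Apply the rule to the run-in and to every monthly reading. Report excluded days by arm, and add a sensitivity analysis of Aim 3 that counts all days.

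The cost is protocol wording and slightly more scoring work; the study coordinator already opens the EMR before each monthly download, so checking dates adds little. A few genuinely unusual misses outside a qualifying episode would count as missed.
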